	6.1 Software
	6.2 Calculating z-scores
	6.3 Multiple comparisons
	6.4 Confidence intervals
	6.5 Interaction and effect modification
	6.6 Covariate adjustment
7.	References
8.	Tables
	Table 1 Comparison of developmental scores in the intervention groups at 18 months
	Table 2 Prevalence of developmental delay at 18 months of age 11

1. Study objectives

The main aim of the trial was to assess the safety and impact of supplementation with Lipidbased Nutrient Supplements (LNS) on linear growth of infants and young children and to identify individual, household, and village-level characteristics that modify the effects of LNS on child growth. A secondary aim is to similarly study the impact of LNS on various other (secondary) outcomes in the same target group.

The aim of the secondary analyses described in this appendix is to compare infants in 6 different intervention groups: dietary supplementation from age 6 to 18 months with 10 g, 20 g or 40 g per day milk-containing LNS, or 20 g or 40 g per day milk-free LNS, or nothing (delayed intervention) on the following outcomes:

- 1. 18-month motor development, language development, socio-emotional development, executive function, and interaction with caregivers
- 2. Prevalence of severe and moderate to severe delay in motor development, language development, socio-emotional development, and executive function

2. Hypotheses to be tested

- 1. 18-month scores in gross and fine motor development, language development, socioemotional development, executive function, and interaction with caregivers of infants provided with 10, 20, or 40 g/day of LNS from 6 to 18 months of age will be greater than that of infants who receive no dietary intervention at the same age.
- 2. 18-month scores in gross and fine motor development, language development, socioemotional development, executive function, and interaction with caregivers of infants receiving 20 or 40 g/day of LNS without milk from 6 to 18 months of age will not be lower than that of infants receiving a comparable intervention with milk-containing LNS.
- 3. 18-month scores in gross and fine motor development, language development, socioemotional development, executive function, and interaction with caregivers of infants provided with 20 or 40 g/day of LNS from 6 to 18 months of age will be greater than that of infants who receive 10g/day and that of infants provided with 40 g/day will be greater than that of infant who receive 20 g/day.
- 4. Hypotheses 1-3 will also be examined with regard to the prevalence of severe and moderate to severe delay in motor development, language development, socio-emotional development, and executive function.

3. Definition of the 18-month developmental outcomes

The gross motor score is calculated as the sum of 35 Kilifi Developmental Inventory (KDI) gross motor items, each scored 0 or 1 (sum of *Form 25a Q 5.1-5.2* and *5.6-7.12*). Severe delay is defined as the bottom 10% of our sample. Moderate to severe delay is defined as the bottom 25% of our sample.

The fine motor score is calculated as the sum of 34 KDI fine motor items, each scored 0 or 1 following Abubakar et al. (2008). Severe delay is defined as the bottom 10% of our sample. Moderate to severe delay is defined as the bottom 25% of our sample.

The psychomotor score is calculated as the sum of 69 KDI fine and gross motor items, each scored 0 or 1. Severe delay is defined in two ways: (1) the bottom 10% of our sample and (2) <-3 SD below the mean according to published norms from Kenya (Abubakar et al. 2008). Moderate to severe delay is defined in two ways: (1) the bottom 25% of our sample and (2) <-2 SD below the mean according to published norms from Kenya (Abubakar et al. 2008).

Language development is quantified as

- a. Vocabulary score, calculated as the sum of *Form 25c LANGVOCAB1* through *LANGVOCAB100*. Severe delay is defined as the bottom 10% of our sample.
 Moderate to severe delay is defined as the bottom 25% of our sample.
- b. Expressive vocabulary > 10 words vs. <= 10 words, derived from the vocabulary score
- c. Word combining (Has the child started combining words into sentences? 0 = not yet, 1 = sometimes, 2 = often) *Form* 25*c* Q 4.1

Socio-emotional development is calculated as the sum of *Form 25b PSED1* through *PSED19*. Severe delay is defined as the top 10% of our sample (a lower score indicates more advanced socio-emotional development). Moderate to severe delay is defined as the top 25% of our sample.

Executive function is calculated as

- a. A not B task total number correct, *Form 25a Q16.2*. Severe delay is defined as the bottom 10% of our sample. Moderate to severe delay is defined as the bottom 25% of our sample.
- b. A not B task total errors after set 1, Form 25a Q16.3
- c. A not B task total trials completed, *Form 25a Q 16.1*. If this variable is not normally distributed, another statistical approach will be used, such as creating a dichotomous variable

Interaction with caregivers is calculated as the sum of the activities with adults in the past three days (*Form 25d Q 4.1.1* through Q 4.5.3).

4. Basis for the analysis: Intention to treat and per protocol

The basis for the analysis will be the same as that for the primary outcomes.

5. Presentation of the study findings and hypothesis testing

5.1 Comparison of the developmental scores at 18 months of age between intervention groups versus the control group

The group means and standard deviations for the gross motor score, fine motor score, psychomotor score, vocabulary score, socio-emotional score, and A not B task total number correct, total errors after set 1, and total trials completed, and the interaction with caregivers score will be presented as indicated in Table 1. Both raw scores and z-scores will be presented. The results of pairwise comparisons will be indicated by superscripts. Means that are significantly different from each other will be marked by different letters (e.g., a and b). Means that are not significantly different from each other will be marked by the same letter.

We will use a one-factor analysis of variance (ANOVA) (or ANCOVA in analyses that include covariates, as specified in section 6.6) to test for differences between the six groups. If the group effect is significant at the level of p < .07, we will use Tukey-Kramer's test for post-hoc pairwise comparisons between each intervention group and the control group. The null-hypothesis of LNS having no impact on development will be rejected for each comparison that yields a Tukey-Kramer's adjusted p-value < 0.05.

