Length for age will be determined from age, sex, and length information at six months (visit 0) and 18 months (visit 52) of participant age, using the Stata macro developed by the WHO using the WHO 2006 multi-centre growth standard. The values will be rounded to two decimal points. The change (expressed with two decimals) will be calculated by subtracting the value at 6

months from the value at 18 months of age. *The data will be extracted from Form 00: Q2.5; Form 04: Q1.2, Q2.2*

8 Safety outcomes

Incidence of serious adverse events (SAE) during the observation period.

SAE will be defined as an event determined to be an SAE by the study physician. The SAEs will be categorized into five categories: Death, life threatening event, inpatient hospitalization, significant disability or other serious adverse event. *The data will be extracted from Form 29, Q3.2.*

9 Basis for the analysis: Intention to treat and per protocol

Primarily, the analysis will be based on the principle of modified intention-to-treat. The modification concerns six participants who were accidentally allocated to another group than actually randomized. For each participant, the randomization code was pre-packed and sealed in an individual envelope that was opened and used for group allocation at enrolment. For these 6 individuals, the randomizer made a recording error, i.e. s/he noted down in a data collection form an incorrect group code or wrote the code with unclear handwriting. The incorrect code was later transcribed into the computer software that was used to plan participant visits and allocate interventions. These six participants were told to belong to the erroneously recorded intervention group and they received that intervention throughout the trial – hence they will also be analyzed in that group (rather than the one written on the randomization slip).

All randomized participants are eligible to be included in the analyses, with the exception that subjects with missing data on an outcome variable will be excluded for the analysis of that outcome. For variables targeted to be measured every 6-months, the data are considered missing if the actual measurement date is over +/- 8 weeks from target.

Number of participants with non-missing values analyzed for each end point will be presented by treatment groups.

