6.2 Calculating scores and z-scores

If a large percentage of data is missing for any item, we will exclude that item from the total score. For all other missing item scores, we will impute the scores based on the other items in the same subscale. We will use the imputation method described in Raghunathan et al. (2001).

Z-scores of developmental variables will be calculated based on the distribution of the iLiNS-DOSE sample, by standardizing the distribution to a mean of 0 and standard deviation of 1.

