6.6 Covariate adjustment

The same procedure will be followed as for the main analyses, with three models rather than four models:

1. No covariate adjustment

- 2. Adjustment for child age at developmental assessment
- 3. Adjustment for child age at developmental assessment, baseline LAZ-score, and baseline WHZ-score and for any of the variables presented in tables 1a and 1b of the primary outcome Statistical Analysis Plan (SAP) showing statistically significant association (at p<0.1 level) with the developmental score

In addition to the variables in tables 1a and 1b of the primary outcome SAP, we will consider the following variables for inclusion:

- 1. Family care indicators score, if this score is not different between supplement groups.
- 2. For the KDI scores, the child's mood, interaction with the tester, and activity level during testing, if they are not different between supplement groups (*Form 25a Q 3.1 3.3*).
- 3. For the language scores, the child's primary language (Chichewa, Chiyao, English, or other) and the number of languages to which the child had been exposed (*Form 25c Q* 1.7-1.8).

7. References

- Kleinman, L. C., & Norton, E. C. (2009). What's the Risk? A simple approach for estimating adjusted risk measures from nonlinear models including logistic regression. *Health services research*, *44*(1), 288-302.
- Raghunathan, T. E., Lepkowski, J. M., Van Hoewyk, J., & Solenberger, P. (2001). A multivariate technique for multiply imputing missing values using a sequence of regression models. Survey Methodology, 27(1), 85-95.

8. Tables

Table 1 I	Results of the	ANCOVA com	paring developmenta	al scores in the intervent	ion groups at age 18 months.
10010 1 1	Leoseries or ente				Tom groups at age to monthly

Variable	Control	10g milk	20g milk	20g milk-	40g milk	40g milk-	P-value
		LNS	LNS	free LNS	LNS	free LNS	
Mean gross motor raw score (SD) ^y	xx.x ^x (xx.x)	xx.x ^x (xx.x)	$xx.x^{x}(xx.x)$	$xx.x^{x}(xx.x)$	$xx.x^{x}(xx.x)$	$XX.X^{X}(XX.X)$	X.XX
Mean gross motor z-score (SD) ^y	$xx.x^{x}(xx.x)$	$xx.x^{x}(xx.x)$	$xx.x^{x}(xx.x)$	$xx.x^{x}(xx.x)$	$xx.x^{x}(xx.x)$	$XX.X^{X}(XX.X)$	

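### Appendix 02 sets its sample-based delay cut-offs and z-scores without regard to age at testing and lets a 10% rule decide whether age-adjusted results are tabulated

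*SAP*

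**What the plan says.** Appendix 02, section 3, defines gross motor, fine motor, vocabulary and A-not-B delay by rank in the trial sample: "Severe delay is defined as the bottom 10% of our sample" and "Moderate to severe delay is defined as the bottom 25% of our sample". For the socio-emotional score, where lower is better, the tail is reversed: "Severe delay is defined as the top 10% of our sample". Psychomotor delay has the sample-based definition and a second, external one: "2) <-3 SD below the mean according to published norms from Kenya" (and 2 SD for moderate to severe). None of the sample-based definitions mentions age.

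Section 6.2 is also silent on age: "Z-scores of developmental variables will be calculated based on the distribution of the iLiNS-DOSE sample".

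Age enters in section 6.6. Model 1 is unadjusted, model 2 is "Adjustment for child age at developmental assessment", and model 3 adds baseline LAZ, baseline WHZ and selected covariates. Section 5.1 applies the covariates by ANCOVA, and section 5.4 sends delay prevalence through logistic regression in the same way. The choice between models follows main SAP section 12.6: an adjusted analysis is presented as primary if a group coefficient moves by more than 10%. Otherwise the tables show unadjusted results and the fullest model goes in the text.

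For timing, Appendix 02 section 4 adopts the main basis for analysis. Main SAP section 9 says of six-monthly variables that "the data are considered missing if the actual measurement date is over +/- 8 weeks from target".

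**The concern.** The motor and vocabulary outcomes are counts of items passed or words used. A count of this kind can be expected to rise with age around 18 months. If so, a child tested early is more likely to fall in the worst 10% than an equally able child tested late, and the label mixes ability with test date.

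Age at testing does vary. Appendix 05 states that infants were enrolled at 5.5 to 6.5 months, that visit 52 was planned one year after enrolment, and that many endline visits were late. If developmental testing followed visit 52, even punctual tests span a month of age.

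Two things are at stake. Hypothesis 4 of Appendix 02 rests on the delay label, and readers will take the Table 3 proportions as developmental delay. Separately, whether Tables 1 to 3 show age-adjusted results is left to a change-in-estimate rule, while the shell of Table 1 is already titled as an ANCOVA and footnoted for covariates.

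**Working it through.** The SAP gives no power or error rate for these outcomes, so there is no figure to reproduce. It gives neither the score gain per month nor the observed spread of age at testing, so both are assumed below and the results are illustrative.

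**Inputs**
- From the SAP: 1932 infants in six groups, cut-offs at 10% and 25%, a milk non-inferiority margin of 0.2 z, and a window of at most ±8 weeks.
- Assumed: equal groups before dropout, 1932 / 6 = 322 per arm; a gain of 0.05 to 0.30 within-age SD per month; and three age spreads (uniform ±4 weeks, normal with SD 3 weeks truncated at 8, uniform ±8 weeks).

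**1. Who is labelled.** Simulate 2,000,000 children with score = slope × age + N(0,1). Compare the pooled cut-off with the same cut-off on the age-adjusted residual. The last two columns give the share of labelled children who would lose the label, for slopes of 0.05 to 0.30.

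| Age spread | Severe delay, youngest vs oldest quarter tested (slope 0.2) | Severe labels lost | Moderate-to-severe labels lost |
|---|---|---|---|
| uniform ±4 weeks | 12.5% vs 7.7% | 2% to 12% | 1.5% to 9% |
| normal, SD 3 weeks | 13.3% vs 7.1% | 2% to 14% | 2% to 10% |
| uniform ±8 weeks | 15.1% vs 5.7% | 4% to 23% | 3% to 17% |

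Age as a covariate in a logistic model leaves these labels, and the raw proportions in Table 3, as they are.

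**2. Precision.** In the simulation age explains 0.1% to 9% of score variance. Take a true shift of 0.25 within-age SD, the 25% cut-off and 322 per arm. If age explains a share R² of variance, the shift on the pooled scale is 0.25 × √(1 − R²).
- R² = 0: 25% against 17.8%, power 61%.
- R² = 0.05: 25% against 17.9%, power 59%.
- R² = 0.10: 25% against 18.1%, power 57%.

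**3. Bias by chance.** The 95% limit for a difference in mean age between two arms is 1.96 × SD × √(2/322). For SDs of 2.3, 3 and 4.62 weeks (the three spreads) this is 0.36, 0.46 and 0.71 weeks. At 0.2 SD per month and 4.345 weeks per month, the shift is 0.016, 0.021 and 0.033 SD. The milk contrast normally pools two arms per side, so √(2/644) applies: 0.25, 0.33 and 0.50 weeks, or 0.012, 0.015 and 0.023 SD against the 0.2 margin.

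**4. The 10% rule.** The threshold is relative to the unadjusted coefficient. For an illustrative coefficient of 0.05 SD it is 0.1 × 0.05 = 0.005 SD, which the shifts in step 3 pass easily. For 0.25 SD it is 0.025 SD, which they mostly do not reach. Whether age-adjusted results are tabulated therefore depends largely on how big the effect happens to be. Precision, the main reason to adjust a randomised comparison for age, plays no part in the rule.

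**5. Z-scores.** Pooled standardisation is a linear rescaling. With age in the model the contrast is age-adjusted and only the SD unit is wider. At R² = 0.092 the factor is 1/√(1 − 0.092) = 1.05, about 5%.

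**The case against.** The strongest reply is that the plan does handle age. Age at assessment is the only covariate in model 2 and is also in model 3, for scores and delay alike. Table 1 is titled as an ANCOVA with covariate footnotes, and section 5.4 cites a method for adjusted risk measures. If arms differed in lateness enough to matter, the 10% rule would usually bring the adjusted analysis forward. Psychomotor delay also has an external-norm definition, and the ±8 weeks is a cap on six-monthly variables, not an observed spread.

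Most of this stands. A reader might infer that Appendix 02 ignores age, or that its comparisons between arms are biased. The documents support neither: age is a planned covariate, and randomisation balances test timing up to chance unless timing itself depends on arm. Nor do they show that every score rises with age. The caregiver-interaction score, for instance, counts adult activities and has no delay cut-off.

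The reply leaves two points open. Covariates do not repair the label, and the table shells and the 10% rule can call for different models in the same table. If the rule is triggered, it also does not say which adjusted model is shown.

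**Conclusion.** The point holds in limited form. The sample-based delay cut-offs and the z-scores are blind to age as written, and the model to be tabulated is not fixed. The main consequence is misclassification: 2% to 23% of severe-delay labels under the assumed slopes and spreads. With it comes a modest loss of precision, about four percentage points of power near the upper end of the assumed range.

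More alarming figures can be produced but should not be relied on. With a slope of 0.40 SD per month, a child tested 8 weeks (1.84 months) early has a probability of Φ(−1.2816 + 0.74) = 29% of a severe-delay label, and a one-week difference in mean test age (0.23 month) uses 0.23 × 0.40 / 0.2 = 46% of the margin. The first needs the steepest slope and a child at the very edge of the window. The second needs that slope and an imbalance larger than the chance limits in step 3. The SAP supports neither.

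These are secondary outcomes, and the true size cannot be found from the SAP. The change is worth making because it is free.

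**What to change.** - **Appendix 02, section 3.** For the ability scores that depend on age, listed by name in advance, define the sample-based cut-offs on scores adjusted for exact age at assessment. One way is to regress each score on age in the whole sample without group information, standardise the residuals, and take the worst 10% and 25% (the top tail for the socio-emotional score, if listed). A score unrelated to age would keep nearly the same ranking. Leave the external-norm psychomotor definition as it is, and state whether those norms are age-specific.
- **Appendix 02, section 6.6.** Name model 2 in advance as the base model for Tables 1 to 3, with model 1 as a sensitivity analysis, and drop the 10% rule for this choice. This also brings the text into line with the title of Table 1.

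The cost is SAP wording only. Age at assessment is already a planned covariate, so no new data are needed.

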5.2 Comparison of milk-containing and milk-free LNS

We will use a two-factor ANOVA/ANCOVA with main effects of dose of LNS (0g, 10g, 20g, or 40g) and milk (yes or no) and the dose by milk interaction. The control and 10g LNS groups will be treated as containing milk. This means that the main effect of milk and the dose by milk interaction are calculated in the model using the data from the 20g and 40g groups only.

If the dose by milk interaction is not significant at the level of p < 0.1, we will conclude that the effect of milk does not differ between the 20g and 40g groups. In this case, the difference in mean scores between the milk-containing and milk-free LNS will be presented as shown in Table 2. A 90% CI will be created for the milk effect, which will be the average of the individual milk effects for the 20g and 40g groups. The set non-inferiority margin for this analysis will be 0.2 Z-score units. If the lower bound of the 90% CI of the coefficient is larger than -0.2, non-inferiority is confirmed. If

the upper and lower bounds of the 90% CI are larger and smaller, respectively, than -0.2, the finding is not conclusive.

If the dose by milk interaction is significant at the level of p < 0.1, we will examine the effect of milk separately in the 20g and 40g groups. In this case, the difference in mean scores between the milk-containing and milk-free LNS will be presented in an expanded version of Table 2 which will present the coefficient, 90% confidence interval, and p-value for (1) the difference in scores in 20g/day LNS with milk versus 20g/day LNS without milk, (2) the difference in scores in 40g/day LNS with milk versus 40 g/day LNS without milk 40g, and (3) the dose by milk interaction term. In this case, a 90% CI will be created for each of the individual milk effects for the 20g and 40g groups. The set non-inferiority margin for this analysis will be 0.2 Z-score units. If the lower bound of the 90% CI of the coefficient is larger than -0.2, non-inferiority is confirmed. If the upper bound of the 90% CI are larger and smaller, respectively, than -0.2, the finding is not conclusive.

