5.3 Comparison of the 10g, 20g, and 40g LNS groups

If the dose by milk interaction is significant at the level of p < 0.1, we will use Tukey-Kramer's test for post-hoc pairwise comparisons between each intervention group in the one-factor ANOVA/ANCOVA described in section 5.1. The null-hypothesis of higher doses of LNS having no impact compared to lower doses will be rejected for each comparison that yields a Tukey-Kramer's adjusted p-value < 0.05.

If the dose by milk interaction is not significant at the level of p < 0.1 and if we conclude that LNS without milk is not inferior to milk-containing LNS, we will use Scheffe test in the one-factor ANOVA/ANCOVA described in section 5.1 to compare the mean scores among the combined 40g group (with and without milk), the combined 20g group (with and without milk), the 10g group, and the control group. The null-hypothesis of higher doses of LNS having no impact compared to lower doses will be rejected for each comparison that yields a Scheffe's adjusted p-value < 0.05.

If the dose by milk interaction is not significant at the level of p < 0.1 and if we do not conclude that LNS without milk is not inferior to milk-containing LNS, we will use Tukey-Kramer's test for post-hoc pairwise comparisons between each intervention group in the two-factor ANOVA/ANCOVA described in section 5.2. This model calculates the effect of dose while controlling for the effect of milk. The null-hypothesis of higher doses of LNS having no impact compared to lower doses will be rejected for each comparison that yields a Tukey-Kramer's adjusted p-value < 0.05.

5.4 Prevalence of severe and moderate to severe developmental delay The proportions of children demonstrating severe and moderate to severe developmental delays at age 18 months will be presented as shown in Table 3. We will use logistic regression, following the same approach outlined in sections 5.1 through 5.3. The results of pairwise comparisons will be indicated by superscripts. Relative risks and confidence intervals will be calculated based on the method described in Kleinman (2009).

6. General notes on statistical methods

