Difference in mean fine motor z-score in milk-free LNS compared to milk-containing LNS	XX.XX	xx.xx to xx.xx	X.XX
Difference in mean psychomotor z-score in milk-free LNS compared to milk-containing LNS	XX.XX	xx.xx to xx.xx	X.XX
Difference in mean vocabulary z-score in milk-free LNS compared to milk-containing LNS	XX.XX	xx.xx to xx.xx	X.XX
Difference in mean socio-emotional z-score in milk-free LNS compared to milk-containing LNS	XX.XX	xx.xx to xx.xx	X.XX
Difference in mean A not B task total correct z-score in milk-free LNS compared to milk-containing LNS	XX.XX	xx.xx to xx.xx	X.XX
Difference in mean A not B task errors z-score in milk- free LNS compared to milk-containing LNS	XX.XX	xx.xx to xx.xx	X.XX
Difference in mean A not B task total trials z-score in milk-free LNS compared to milk-containing LNS	XX.XX	xx.xx to xx.xx	X.XX
Difference in mean interaction with caregivers z-score in milk-free LNS compared to milk-containing LNS	XX.XX	xx.xx to xx.xx	X.XX

Table 2. Regression results of the difference between the milk-containing and milk-free LNS

	Control	10g milk	20g milk	20g milk-	40g milk	40g milk-	P-	7
age.								
Table 3 Results of the logistic regressio	n comparing	g the prevalenc	e of developme	ental delay in th	e intervention	n groups at 18 i	months c	of

Variable	Control	10g milk LNS	20g milk LNS	20g milk- free LNS	40g milk LNS	40g milk- free LNS	P- value
Proportion severe gross motor delay, No. /total	xxx/xxx	xxx/xxx	xxx/xxx	xxx/xxx	xxx/xxx	xxx/xxx	X.XX
No. (%)	$(xx.x\%)^x$	(xx.x%),	(xx.x%),	(xx.x%),	(xx.x%),	(xx.x%),	
Relative risk (95% CI)		x.xx (x.xx- x.xx) ^x					
Proportion moderate to severe gross motor	xxx/xxx	xxx/xxx	xxx/xxx	xxx/xxx	xxx/xxx	xxx/xxx	X.XX
delay, No. /total No. (%)	$(xx.x\%)^x$	(xx.x%),	(xx.x%),	(xx.x%),	(xx.x%),	(xx.x%),	
Relative risk (95% CI)		x.xx (x.xx- x.xx) ^x					
Proportion severe fine motor delay, No. /total	xxx/xxx	xxx/xxx	xxx/xxx	xxx/xxx	xxx/xxx	xxx/xxx	X.XX
No. (%)	$(xx.x\%)^x$	(xx.x%),	(xx.x%),	(xx.x%),	(xx.x%),	(xx.x%),	
Relative risk (95% CI)		x.xx (x.xx- x.xx) ^x					
Proportion moderate to severe fine motor delay,	xxx/xxx	xxx/xxx	xxx/xxx	xxx/xxx	xxx/xxx	xxx/xxx	X.XX
No. /total No. (%)	$(xx.x\%)^x$	(xx.x%),	(xx.x%),	(xx.x%),	(xx.x%),	(xx.x%),	
Relative risk (95% CI)		x.xx (x.xx- x.xx) ^x					
Proportion severe psychomotor delay, No. /total	xxx/xxx	xxx/xxx	xxx/xxx	xxx/xxx	xxx/xxx	xxx/xxx	X.XX
No. (%)	$(xx.x\%)^x$	(xx.x%),	(xx.x%),	(xx.x%),	(XX.X%),	(xx.x%),	
Relative risk (95% CI)		x.xx (x.xx- x.xx) ^x					

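### Appendix 02, section 5.2: one lower-bound non-inferiority rule for all nine scores points the wrong way for the socio-emotional score and, by inference, for A-not-B errors

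*SAP*

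**What the plan says.** All references are to SAP Appendix 02 unless stated.

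- **Rule.** Section 5.2 sets a single margin, "The set non-inferiority margin for this analysis will be 0.2 Z-score units", and a single criterion, "If the lower bound of the 90% CI of the coefficient is larger than -0.2, non-inferiority is confirmed". Neither varies by outcome.
- **Contrast.** Table 2 lists nine z-scores, each as milk-free compared to milk-containing. They include "Difference in mean socio-emotional z-score in milk-free LNS compared to milk-containing LNS" and "Difference in mean A not B task errors z-score in milk- free LNS compared to milk-containing LNS".
- **Direction of the scores.** Section 3 notes for the socio-emotional score that "a lower score indicates more advanced socio-emotional development", and so takes delay from the top of the distribution. It also lists "A not B task total errors after set 1" as an executive-function measure, without stating a direction.
- **Standardisation.** Section 6.2 scales each score to mean 0 and SD 1. It reverses none of them.
- **Hypothesis.** Hypothesis 2 in section 2 says that scores without milk will not be lower, for every domain including the socio-emotional one.
- **Use of the verdict.** Where the interaction is not significant, section 5.3 uses the non-inferiority conclusion to choose between a Scheffé comparison with milk and milk-free arms combined and a two-factor model that controls for milk.
- **Delay.** For delay prevalence, section 5.4 says: "We will use logistic regression, following the same approach outlined in sections 5.1 through 5.3".

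**The concern.** A lower-bound rule protects against harm only when a negative coefficient means harm. That is so for the motor, vocabulary, total-correct and caregiver-interaction scores. It is not so for the socio-emotional score, nor for the number of errors. There, harm from removing milk gives a positive coefficient, which a limit of -0.2 can never catch, while a real benefit is what pushes the lower bound below -0.2.

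Section 3 shows that the authors knew the direction of the socio-emotional score, since they reversed its delay cut-offs. The adjustment was not carried into section 5.2. An analyst who follows the text would report milk-free LNS as non-inferior on a score where it could be clearly worse, and would take that conclusion into the choice of dose model. According to section 6 of the main SAP, secondary analyses will mostly be done by investigators who are not study statisticians, so an unwritten correction cannot be relied on.

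**Working it through.** The appendix gives no sample size, power or error rate for this analysis, so there is no figure of its own to reproduce. What can be checked is how the rule behaves on a score where higher is worse.

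**Inputs**
- Margin 0.2 and limit -0.2: section 5.2.
- Confidence level 90% (section 5.2), so the one-sided error is (1 - 0.90)/2 = 0.05 and the multiplier is 1.645. In the no-interaction branch the interval is taken over both doses: "A 90% CI will be created for the milk effect, which will be the average of the individual milk effects for the 20g and 40g".
- SD = 1: section 6.2.
- 1932 children in six groups: main SAP, section 2. *Assumed* equal: 1932/6 = 322 per group, or 2 × 322 = 644 per milk arm over the two doses.
- Share with developmental data: not given. *Assumed* 60% to 100%, that is 193 to 322 per group and 386 to 644 per pooled milk arm.

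**Formulas** (normal approximation; d = true milk-free minus milk-containing difference; n = children per milk arm)
- SE = √(2/n); half-width of the 90% CI = 1.645 × SE.
- Rule as written: P(lower bound > -0.2) = Φ((d + 0.2)/SE - 1.645).
- Mirrored rule for a higher-is-worse score: P(upper bound < +0.2) = Φ((0.2 - d)/SE - 1.645).

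**One case in full.** With n = 644, SE = √(2/644) = 0.056 and the half-width is 0.092. At d = +0.2 the expected CI is 0.108 to 0.292. The rule as written passes with probability Φ(0.4/0.0557 - 1.645) = Φ(5.5) = 1.000. The mirrored rule gives Φ(-1.645) = 0.050. At d = +0.3 the expected CI is 0.208 to 0.392, wholly beyond the margin on the harmful side, and the written rule still confirms non-inferiority.

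**Probability of declaring non-inferiority on a higher-is-worse score**

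| n per milk arm | SE | Half-width | Written, d = +0.2 | Mirrored, d = +0.2 | Written, d = -0.3 | Mirrored, d = -0.3 | Either rule, d = 0 |
|---|---|---|---|---|---|---|---|
| 644 (pooled, 100%) | 0.056 | 0.092 | 1.000 | 0.050 | 0.0003 | 1.000 | 0.974 |
| 386 (pooled, 60%) | 0.072 | 0.118 | 1.000 | 0.050 | 0.0012 | 1.000 | 0.872 |
| 322 (one dose, 100%) | 0.079 | 0.130 | 1.000 | 0.050 | 0.0018 | 1.000 | 0.814 |
| 193 (one dose, 60%) | 0.102 | 0.167 | 0.989 | 0.050 | 0.0043 | 1.000 | 0.626 |

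The single-dose rows apply in the significant-interaction branch if its contrast is read as in Table 2.

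**Where the rules agree.** Both confirm non-inferiority when the estimate lies within ±(0.2 - half-width): ±0.108 at n = 644 and ±0.033 at n = 193. They part company outside that band.

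**Sign in the interaction branch.** When the interaction is significant, section 5.2 names the milk-containing product first in each contrast, the opposite of Table 2. Taken literally, the rule would then be right for the two scores at issue and wrong for those where higher is better. The same sentence calls the display an expanded Table 2, so the intended sign is unclear.

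**The case against.** **The analyst would reverse the scores anyway.** Section 3 shows awareness of the direction. But no part of the appendix reverses a score or mirrors the rule, and a sign changed once results are visible is an undocumented change to a decision rule. Elsewhere the SAP does attend to direction: Appendix 08, where higher is worse, and Appendix 03, where the contrast is control minus intervention, both judge by the upper bound.

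**Only one score is reversed by explicit text.** This stands. The direction of the error count is inferred from what it measures. The inference is a safe one, but the plan should state it. The direction of total trials completed is also unstated.

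**The rule does not always give the wrong answer.** This also stands. With no true difference, the written and mirrored rules pass equally often.

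**The outcomes are secondary.** True. The non-inferiority rule for change in LAZ in section 11.4 of the main SAP has the correct sign and is untouched.

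A reader might go further than the documents allow in three ways:
- *That milk-free LNS is harmful on these scores.* Nothing in the SAP says so. The point is conditional: harm, if present, would pass.
- *That every delay outcome gets a reversed verdict.* Hypothesis 4 does extend hypothesis 2 to delay, but a margin in z-score units has no defined meaning in a logistic model, and Table 3 shows no milk-free contrast. The margin is undefined, so there is no verdict to reverse.
- *That the tests of hypothesis 1 are affected.* Its wording has the same slip of direction, but section 5.1 tests it by ANOVA and Tukey-Kramer comparisons, which do not depend on the sign of the score.

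**Conclusion.** The rule in section 5.2 is wrong as written for two of the nine Table 2 scores: the socio-emotional score on the plan's own statement, and A-not-B errors by the nature of the measure. On these, a true harm at the margin is confirmed as non-inferior with probability 0.99 to 1.00 instead of 0.05, and a true benefit of 0.3 SD passes in fewer than 1 in 200 trials.

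The probabilities rest on equal groups, 60% to 100% availability of data, SD 1 and a normal approximation. The direction of the error rests on none of these. The consequence reaches past the label, because the verdict selects the dose model in section 5.3. The other clearly directed scores are handled correctly as long as the contrast is the one in Table 2, which the interaction branch leaves in doubt.

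**What to change.** 1. **Section 5.2.** State the contrast as milk-free minus milk-containing in both the interaction and the no-interaction branch. This comes first, because reversing the scores under the opposite contrast would make these two wrong again.
2. **Section 6.2.** Multiply the socio-emotional and A-not-B error z-scores by -1 before the rule is applied, with a table footnote because Table 1 shows raw scores beside the z-scores. Alternatively, leave the scores alone and require the upper 90% bound to be below +0.2 for these two.
3. **Section 3.** State in words which direction is better for A-not-B errors and for total trials completed.
4. **Section 2.** Reword hypothesis 2 as not worse.
5. **Section 5.4.** Report relative risks with CIs for delay and make no non-inferiority claim, unless a separate margin on a suitable scale, with an upper-bound criterion, is set in advance.

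Items 1 to 4 cost a few sentences, a footnote and a line of code, and need no further data. Item 5 costs nothing if the claim is dropped. Choosing a margin for delay would be a substantive decision that needs its own justification.
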